#### 6.1.1 Sample and population of the study

This research will be carried out at one prison unit, located in the city of Dourados, in the state of Mato Grosso do Sul. Currently, this prison unit has approximately 2,300 inmates, with a mean age of  $31.5 \pm 9.4$  years; an average of  $9.7 (\pm 4.2)$  individuals per cell, who remain in a closed regimen, about  $20.8 (\pm 24.1)$  months. The TB indicators show a tuberculin test seroconversion rate of 26% (23-26) and incidence, 2.45 / 100,000(28).

The sample was calculated for a significance level of 5%, detection power of 90%, considering a percentage of occurrence of latent TB of 20% in the control group after one year of follow-up and 10% in the experimental group. For these parameters, 560 individuals will be needed for the study, however, 30% will be added for possible losses, ending the sample in 728 participants. Memory calculation available at <https://www.sealedenvelope.com/power/binary-superiority/>.

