At follow-up visits of 6, 12 and 24 months, if the interferon gamma result is indeterminate, the participant remains in the clinical trial and a new sample is collected within 30 days. If the IGRA result is positive (result standardized according to the package insert of the Qiagen®), the participant will suspend the medication (in the case of the 6-month visit), will be excluded from the study and treatment for latent TB.

If the sputum culture is positive for Mtb, the participant will be excluded from the study and treatment for active TB according to MS will be offered. If the sputum culture is contaminated, a new sample should be collected within 30 days after the result.

In the occurrence of hepatotoxicity, diagnosed through hepatic enzyme levels (elevation greater than five times the upper limit of the test if the individual is asymptomatic) and / or clinical examination (presence of jaundice, right upper quadrant pain, dark urine, fever, asthenia, myalgia), the intervention will be interrupted and the participant will be led to clinical care by the project team, according to the project's SOP. In this study, the following values will be used as laboratory parameter: AST: 8-40 IU / mL and ALT: 5-30 IU / mL(54,55). Other laboratory tests may be

requested from the research participants, according to the clinical judgment of the physician responsible for the care of the AE and according to the specific SOP of the project.

IGRA, smear culture, and serology for HIV, hepatitis B and C are performed LPCS / UFGD. The AST/ALT exams and other laboratory tests, when necessary, are performed in an external laboratory.

During the course of the study, the Notification of Injury Information System will be used to identify the occurrence of active TB cases in both groups.

The box below summarizes the activities to be developed at each stage of the protocol.

	Enrollment	DOT start (D0)	1 st visit (3 mo± 15 d)	2 nd visit (6 mo± 15 d)	3 rd visit (9 mo± 15 d)	4 th visit (12 mo± 30 d)	5 th visit (24 mo± 30 d)	Early exclusion visit
Consent process	X							
Verification of inclusion and exclusion criteria	X							
AUDIT	X							
Medical history	X							
Criminal history	X							
Randomization		X						
DOT star		X						
DOT end						X		
IGRA	X			X		X	X	(X)
ALT, AST	X		X	X	X	X		(X)
Another laboratory exams	(X)		(X)	(X)	(X)	(X)		(X)
Anti-HIV, HBsAg e Anti-HCV	X							(X)
Sputum coleccion	X			X		X	X	(X)

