## 6.6 Estatistical analysis

Data on demographic, socioeconomic, medical and criminal history, as well as on pre, intra and post-intervention laboratory tests will be stored online at REDCap, available at <<http://www.matogrossodosul.fiocruz.br/redcap/>>, where each researcher is identified by single user and password, guaranteeing restricted and confidential access. Statistical analysis will be done with IBM® SPSS Statistics software.

The incidence will be calculated on the basis of the new cases detected during the follow-up period, per 100 person-years. It will be considered a new case of TB individuals, regardless of the group, who present bacilloscopy or positive culture. For latent TB, a seroconversion will be considered for individuals who exhibit interferon gamma levels above the upper limit considered by the manufacturer of the QuantiFERON® TB Gold Plus commercial test in the 12th or 24th month.

The effect of the intervention will be calculated through Relative Risk (RR), considering a Confidence Interval of 95% (95% CI). To determine the effectiveness of the intervention will be used Relative Risk Reduction (RRR) and Absolute Risk Reduction (RAR). In addition, to measure the impact of the intervention, the Number Needed to Treat (NNT) will be calculated.

Two protocols will be performed for statistical analysis: 1) intention-to-treat analysis and 2) per protocol. The sample calculation for the primary outcomes is based on intention-to-treat analysis.

The intent-to-treat analysis will be performed for all subjects who complete at least 6 months of treatment. The participant may decide to withdraw the consent in whole or in part. In the case of withdrawal of partial consent IGRA will be withdrawn at the 12th or 24th month and the participant will remain in the study according to the initial randomization.

Analysis by protocol will be performed only using the group of individuals who completed at least 80% of the predicted doses of the study.

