## 6.7 Interim analysis

After a 6-month visit of at least 100 participants, in addition to the follow-up clinic-laboratorial evaluation (which includes blood collection for hepatic enzyme dosage and directed clinical examination), an evaluation of the effectiveness of the intervention will be carried out, through sputum culture and interferon-gamma dosing / quantification. It is estimated that there is a linear relationship between follow-up time and the risk of acquisition of latent TB.

This evaluation intends to verify the feasibility of continuity of the study and adequacy of the sample calculation. The study will be discontinued if the primary endpoint is less than 2.5% as compared to the control group, or if the difference between the intervention group and the control group is greater than 12.5% according to the box below:

	Intervention (isoniazid) (N=162)	Control (placebo) (N=162)	Finale total number (N final+30%)
Reference	5.0%	10%	726
Insufficient sample	7.5%	10%	3357
Insufficient sample	10.0%	12.5%	3910
Insufficient sample	12.5%	15.0%	4555
Insufficient sample	15.0%	17.5%	5114
Insufficient sample	17.5%	20.0%	5361
Sufficient sample	5.0%	17.5%	172
Sufficient sample	7.5%	20.0%	187
Sufficient sample	10.0%	22.5%	213
Sufficient sample	12.5%	25.0%	218
Sufficient sample	15.0%	27.5%	229

Figura 2 - Sample table of the sample values in both groups (intervention and control), based on the primary outcome.

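### The 80%-of-doses rule makes per-protocol membership depend on the outcome: a month-6 converter cannot qualify, which costs about half of the expected 12-month conversions if month-6 conversions count as primary events

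*Combined protocol and SAP*

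**What the plan says.** Section 6.6 plans two analyses, intention-to-treat and per protocol. For the second: "Analysis by protocol will be performed only using the group of individuals who completed at least 80% of the predicted doses of the study". Section 6.5 sets supervised dosing twice a week for 12 months. It also says that after a positive IGRA "the participant will suspend the medication (in the case of the 6-month visit), will be excluded from the study". A positive sputum culture likewise leads to exclusion from the study.

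No section exempts people who stop because they converted, or limits their predicted doses to the time before conversion.

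On what counts as an event, the text points two ways:

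- Section 6.6 ties latent TB seroconversion to the month-12 or month-24 test and does not name month 6.
- The same section bases incidence on all new cases found during follow-up, and counts active TB (positive smear or culture) with no month restriction.
- Section 6.7 evaluates effectiveness with month-6 IGRA, assumes that "there is a linear relationship between follow-up time and the risk of acquisition of latent TB", and labels Figure 2 as based on the primary outcome.

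**The concern.** A per-protocol set is meant to select on adherence. This one also selects on the endpoint: a participant who took every dose offered and converted at month 6 is removed because the conversion ended dosing. The set then describes only people still free of infection at month 6.

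Per protocol is one of only two planned analyses, and the one a reader will consult for the effect of the drug when taken. Section 6.6 names the absolute risk reduction and NNT as reported measures. Both change if early conversions are missing from the set.

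**Working it through.** **Inputs.** From 6.1.1: "occurrence of latent TB of 20% in the control group after one year of follow-up" and "10% in the experimental group"; "560 individuals will be needed for the study" (280 per arm); "30% will be added for possible losses, ending the sample in 728 participants" (364 per arm). Significance level 5% and power 90%; two-sided testing is my assumption. From 6.5: two doses a week for 12 months, a month-6 visit window of ±15 days, and a repeat sample within 30 days of an indeterminate IGRA. From 6.7: linear risk over time.

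**1. The plan's own sample size.** n per arm = [1.96·√(2·0.15·0.85) + 1.2816·√(0.20·0.80 + 0.10·0.90)]² / 0.10² = 266, or 532 in total. With continuity correction it is 286, or 572 in total, which is 2.1% above the stated 560. Then 560 × 1.30 = 728, as stated.

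**2. What Figure 2 assumes.** Its reference row is 5.0% against 10%, half of the one-year 10% against 20%. Doubling the row's rates and applying the same corrected formula plus 30% gives 744, against the printed 726; undoubled rates give 1,615. Over all 11 rows, doubled rates reproduce nine within 3% (the other two are 3.0% and 4.3% off), and undoubled rates reproduce none. The plan's figures therefore treat month-6 risk as half of month-12 risk.

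**3. Doses.** 2 × 52 = 104 planned. 0.80 × 104 = 83.2, so 84 doses are needed; 0.80 × 12 = 9.6 months. A month-6 converter stops at:

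- month 5.5 (early edge of window): 48 doses, 46%
- month 6: 52 doses, 50%
- month 6.5 (late edge): 56 doses, 54%
- month 7.5 (late visit plus 30-day repeat): 65 doses, 62.5%

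Even measured against a course shortened to 11 months, the last case reaches only 68%. No timing tested reaches 80%.

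**4. Share of events.** At 280 per arm, 12-month conversions are 0.20 × 280 = 56 (control) and 0.10 × 280 = 28 (isoniazid), 84 in all. Under linear risk half fall by month 6: 28 + 14 = 42. A constant hazard gives a share of (1 − √(1 − p))/p, which is 53% for control and 51% for isoniazid.

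**5. Effect on the per-protocol result**, taking month-6 conversions as events and every non-converter as meeting the 80% rule:

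| | All 12-month events | Month-6 converters removed |
|---|---|---|
| Control | 56/280 = 20.0% | 28/252 = 11.1% |
| Isoniazid | 28/280 = 10.0% | 14/266 = 5.3% |
| RR (95% CI) | 0.50 (0.33–0.76) | 0.47 (0.26–0.88) |
| Absolute reduction | 10.0 points | 5.8 points |
| NNT | 10 | 17.1 |
| Power, 280 per arm | 91% | 68% |
| Power, 364 per arm | 97% | 79% |

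Power is Φ[(Δ − 1.96·SE₀)/SE₁], with SE₀ pooled and SE₁ unpooled. At 280 per arm: (0.100 − 1.96 × 0.0302)/0.0299 = 1.37, giving 91%; and (0.0585 − 1.96 × 0.0240)/0.0241 = 0.48, giving 68%.

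**6. If protection differs between half-years.** This is an illustration; the splits are not from the documents. Keep the true 12-month RR at 0.50 and the control risk at 10% in each half.

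- Half-year RRs 0.25 then 0.75: (0.075/0.975)/(0.10/0.90) = 0.69.
- Half-year RRs 0.75 then 0.25: (0.025/0.925)/(0.10/0.90) = 0.24.

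**7. Active TB.** A case whose study drug stops before about month 9.6 also fails the 80% rule, yet 6.6 counts it as a new case. The documents give no assumed active TB risk by arm, so I put no number on this.

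**The case against.** The strongest objection is that 6.6, read literally, counts seroconversion only at month 12 or 24. A month-6 conversion is then not an event in any analysis, and the 80% rule drops no counted primary event by this route. The loss comes instead from the endpoint wording together with the month-6 exclusion, and it reaches intention-to-treat too. With everyone kept in the denominator at 280 per arm, that analysis would show 5% against 10%, with power of about 61%. This stands as far as it goes: a reader might infer that per protocol certainly loses half of the primary events, and the documents do not settle that. It does not rescue the rule. Section 6.7 and Figure 2 rely on month-6 conversions, and if only the endpoint wording were corrected, the 80% rule would remove them again from per protocol. The active TB route does not depend on this ambiguity.

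A reader might also infer a seriously biased relative risk. Under the plan's own linear assumption, with equal protection in both halves, it moves only from 0.50 to 0.47. The values 0.69 and 0.24 rest on splits that no section supports.

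Third, section 6.6 bases the sample size on intention-to-treat and sets no power target for per protocol. That is correct, so the 68% describes lost precision and is not a failure of the trial's sizing.

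Finally, predicted doses might mean doses due up to discontinuation, in which case converters could stay in. The text does not say so; the full 12-month course is the natural reading.

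**Conclusion.** The rule is wrong as written. Every month-6 converter fails it because of the outcome, under every dosing and visit timing tested, and so does any active TB case whose study drug stops before about month 9.6. This conclusion rests only on reading the predicted doses as the full course.

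The size is conditional. If month-6 conversions are primary events and risk is close to linear, about half of the expected 12-month conversions leave the per-protocol set. The harm is then mainly to the absolute reduction, the NNT and precision. The power figures also assume that no one else fails the 80% rule. The relative risk is materially biased only if protection differs between the two half-years.

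The 80% rule does not affect the intention-to-treat analysis, so this is no ground for calling the main analysis invalid.

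**What to change.** In section 6.6:

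- State that a first positive IGRA at month 6 or month 12 counts as a primary event.
- Define the per-protocol set as participants who took at least 80% of the doses scheduled up to the earliest of first positive IGRA, first positive TB result, or month 12. The TB result should come from a sample taken after D0, since a positive enrolment culture marks an ineligible participant.
- State that these participants stay in the set as events, even though section 6.5 ends their follow-up.

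The first change has to accompany the other two; otherwise month-6 converters would be in the set with no event to count.

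The cost is two or three sentences of analysis text, plus dose counts up to the event date. The list of stored data in 6.6 does not mention dose counts, but supervised dosing should provide them; the sponsor should confirm this. Visits, dosing and the handling of positive results are unchanged.

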## 6.7 Interim analysis

After a 6-month visit of at least 100 participants, in addition to the follow-up clinic-laboratorial evaluation (which includes blood collection for hepatic enzyme dosage and directed clinical examination), an evaluation of the effectiveness of the intervention will be carried out, through sputum culture and interferon-gamma dosing / quantification. It is estimated that there is a linear relationship between follow-up time and the risk of acquisition of latent TB.

This evaluation intends to verify the feasibility of continuity of the study and adequacy of the sample calculation. The study will be discontinued if the primary endpoint is less than 2.5% as compared to the control group, or if the difference between the intervention group and the control group is greater than 12.5% according to the box below:

	Intervention (isoniazid) (N=162)	Control (placebo) (N=162)	Finale total number (N final+30%)
Reference	5.0%	10%	726
Insufficient sample	7.5%	10%	3357
Insufficient sample	10.0%	12.5%	3910
Insufficient sample	12.5%	15.0%	4555
Insufficient sample	15.0%	17.5%	5114
Insufficient sample	17.5%	20.0%	5361
Sufficient sample	5.0%	17.5%	172
Sufficient sample	7.5%	20.0%	187
Sufficient sample	10.0%	22.5%	213
Sufficient sample	12.5%	25.0%	218
Sufficient sample	15.0%	27.5%	229

Figura 2 - Sample table of the sample values in both groups (intervention and control), based on the primary outcome.

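### Section 6.7 does not fix the size of its binding interim look: the text allows it from 100 participants in total, while the box behind the stop rule is headed 162 per arm.

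*Combined protocol and SAP*

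**What the plan says.** Section 6.7 calls for an evaluation of effectiveness "After a 6-month visit of at least 100 participants". It gives no upper bound, no date, and no statement that only one comparison will be made.

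The rule is worded as binding: "The study will be discontinued if the primary endpoint is less than 2.5% as compared to the control group". A second condition, on the benefit side, also ends the trial when the observed gap exceeds 12.5 percentage points. Both conditions are tied to a box of scenarios. The two arm columns of that box are headed "Intervention (isoniazid) (N=162") and "Control (placebo) (N=162"), which makes 324 participants.

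The box's Reference row is 5% v 10%. That is half of the 12-month design rates in section 6.1.1 ("percentage of occurrence of latent TB of 20% in the control group after one year of follow-up and 10% in the experimental group"), in line with the linearity assumption in section 6.7: "It is estimated that there is a linear relationship between follow-up time and the risk of acquisition of latent TB".

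The stated purpose is to check whether continuing is feasible and whether the sample size is adequate. No section derives 162, links it to 100, or gives an error rate for the rule.

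**The concern.** The rule compares an observed gap with two fixed limits, so its error rates depend on how many participants contribute to that gap. Against the 560 participants planned before losses, a look at 100 comes at 100/560 = 18% of the sample and a look at 324 at 324/560 = 58%. Both comply with the text.

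The outcome has consequences. Under section 6.8 a stop ends treatment and brings premature exclusion visits. Under section 6.9 a larger than expected benefit ends the experiment and all participants are offered isoniazid. An open-ended trigger also leaves the timing of an efficacy comparison to choice, when it should be set in advance.

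**Working it through.** **Inputs.** Section 6.7: minimum of 100 in total; box headed 162 per arm; limits of 2.5 and 12.5 points; Reference row 5% v 10%. Section 6.1.1: 20% v 10% at 12 months, "significance level of 5%, detection power of 90" per cent, 560 before losses and 728 after adding 30%. Section 6.1.2: two arms of 364.

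**The plan's own sample size.** Two-sided 5% is assumed, since sidedness is not stated.
- n per arm = [1.960·√(2·0.15·0.85) + 1.282·√(0.20·0.80 + 0.10·0.90)]² / 0.10² = 265.9.
- With continuity correction, (n/4)·[1 + √(1 + 4/(n·0.10))]² = 285.5, so 286 per arm and 572 in total. The plan states 560, a difference of 2.1%.
- 560 × 1.30 = 728, as stated.

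**Does the box's final-N column depend on 162?** It does not. The same formula on doubled 6-month rates, times 1.30, gives 744 for the Reference row (box 726), 3910 for 10% v 12.5% (box 3910) and 229 for 15% v 27.5% (box 229). Nine of the 11 rows agree within 3%; the other two are 3.0% and 4.3% off. The figure 162 appears only in the headings.

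**How the limits translate into events.**
- At 50 per arm, one event is 1/50 = 2.0 points. A gap of one event or less stops the trial, two (4.0 points) continue it, and seven (14.0 points) stop it for benefit.
- At 162 per arm, one event is 1/162 = 0.62 points. Four events (2.47) stop, five (3.09) continue, and 21 (12.96) stop for benefit.
- No possible gap equals a limit exactly at either size, so strict or non-strict inequality makes no difference.

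**Standard error of the gap at 5% v 10%.** √[(0.05·0.95 + 0.10·0.90)/n] = 5.2 points at n = 50 and 2.9 points at n = 162.

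**Exact stopping probabilities.** With X the isoniazid count and Y the placebo count, independent binomials with n per arm, the product of their probabilities is summed over all pairs with (Y − X)/n below 0.025 (small-gap stop) or above 0.125 (benefit stop).

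| True 6-month risks (INH v placebo) | Result | 50 per arm | 162 per arm |
|---|---|---|---|
| 5% v 10% (Reference) | small-gap stop | 35.4% | 22.3% |
| | benefit stop | 6.4% | 0.5% |
| | continue | 58.2% | 77.2% |
| 10% v 10% (no effect) | benefit stop | 1.5% | 0.01% |
| | small-gap stop | 69.3% | 79.8% |
| 5% v 17.5% (large effect) | small-gap stop | 5.9% | 0.2% |

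At the Reference row the trial therefore stops at the look 35.4 + 6.4 = 41.8% of the time at 50 per arm and 22.3 + 0.5 = 22.8% at 162.

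**Sizes in between, Reference row.**

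| Per arm | Small-gap stop | Benefit stop |
|---|---|---|
| 75 | 24.1% | 3.8% |
| 100 | 25.0% | 2.3% |
| 125 | 25.4% | 1.4% |

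The small-gap excess is confined to looks near the minimum and is partly an effect of discrete counts. The benefit-stop rate falls over the whole range.

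**Higher background risk, no effect.** A false benefit stop is 3.4% v 0.07% when both risks are 15%, and 5.2% v 0.2% when both are 20%. Doubled, these risks are 30% and 40% at 12 months against the planned 20%, so they lie above the design case.

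**Unequal arms.** Section 6.1.2 uses simple randomization. Averaging over a random split of 100 or 324 participants gives a small-gap stop of 32% v 20% at the Reference row and a false benefit stop of 1.9% v 0.01% with no effect. The picture is the same.

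**The case against.** The strongest reply is that 100 is a minimum, so a look at 324 satisfies both the text and the box. That stands. A reader might infer that the protocol contradicts itself, or that it prescribes a look at 50 per arm. The documents support neither. The 50-per-arm figures describe the earliest look allowed.

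A reader might also infer that the text makes a wrongful small-gap stop much more likely in general. It does not: from about 75 per arm the rate is close to that at 162. If 100 meant per arm, which is not stated, the comparison would be 25% v 22%, although the benefit stop would still be 2.3% v 0.5%.

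The false benefit stop is large as a ratio but modest in absolute terms at the design risk (1.5%). The box promises no error rates and its final-N column does not use 162, so the mismatch does not make those sample sizes wrong, and 324 is not shown to be the intended number.

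It may be said that this is only a feasibility check. Section 6.7 gives that purpose, but it also calls for an evaluation of effectiveness and attaches mandatory discontinuation. Whether 2.5 and 12.5 points are good limits is a separate question. Whatever limits are kept, their behaviour is undefined until the number is fixed.

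**Conclusion.** The point holds as an unfixed interim size with two unreconciled numbers in one section. If the design effect is true, the trial stops at the look about 42% of the time at the earliest permitted size, against 23% at the box's size. Most of that difference comes from small-gap stops close to the minimum. The larger relative change is in benefit stops: about 13-fold at the Reference row, and from 0.01% to 1.5% with no effect.

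These figures assume equal arms (the random-split check agrees), independent participants, and limits read as percentage points of placebo minus isoniazid. They do not show that 324 is correct or that the trial would in practice look at 100. The change should be made because it is cheap and the rule is binding.

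**What to change.** In section 6.7, replace the open-ended minimum with one fixed number of participants with a valid month-6 IGRA, given in total and per arm, and make the box heading agree with it. State that there is one evaluation and no earlier comparison between arms. Report the probabilities of a small-gap stop, a benefit stop and continuation at that number, at least for the Reference row and for no effect.

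The 324 in the sponsor's own box is the natural candidate, but the sponsor must confirm it and give its basis. If the look stays at 100, relabel the box and reset its limits for about 50 per arm.

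The cost is a few sentences and one short table. A look at 324 also comes later and leaves less time to act on the sample-size check. It would use 324/728 = 45% of the enrolment target if nobody were lost. If the whole 30% allowance were lost before month 6 (an assumption), it would use 324 of about 510 remaining (728 × 0.70), or 64%. The documents give no accrual rate, so the delay cannot be put in months. The three-monthly liver-enzyme and clinical checks in section 6.5 are unaffected.

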## 6.8 Study interruption

The study may be terminated early according to the outcome of the interim analysis or at the discretion of the research team, which shall prepare written notices to the IRB and to the sponsor, detailing the reasons interruption of the study.

Participants should be informed about early termination of the study, treatment discontinued, and premature exclusion visit according to figure 1.

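### If the 2.5-point low-gap stop in section 6.7 is obeyed, it wrongly ends about 20–35% of trials in which the planned effect is real and cuts power from about 92% to 61–77%, below the planned 90%

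*Combined protocol and SAP*

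**What the plan says.** - **Planned effect and power (6.1.1).** "The sample was calculated for a significance level of 5%, detection power of 90" per cent, "considering a percentage of occurrence of latent TB of 20% in the control group after one year of follow-up" and 10% under isoniazid. This gives 560 evaluable participants (280 per arm), raised by 30% to 728.
- **Interim look (6.7).** It takes place "After a 6-month visit of at least 100 participants". The box headers instead give 162 in each arm: "Intervention (isoniazid) (N=162").
- **Scaling to 6 months (6.7).** "It is estimated that there is a linear relationship between follow-up time and the risk of acquisition of latent TB". The Reference row is accordingly 5% against 10%.
- **Stopping rule (6.7).** "The study will be discontinued if the primary endpoint is less than 2.5% as compared to the control group". A second arm of the rule stops the study if the difference exceeds 12.5%.
- **Status of the rule (6.8).** "The study may be terminated early according to the outcome of the interim analysis", or at the research team's discretion.

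The protocol gives no confidence limit, conditional power, false-stop probability or power adjustment for the low-gap criterion.

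**The concern.** The sentence is loosely worded, but the box shows what it most naturally means. All five rows marked as having an insufficient sample are exactly 2.5 points apart, and all five marked sufficient are exactly 12.5 points apart, matching the two thresholds in the text. The low cut is therefore an observed absolute difference of 2.5 points at 6 months, half of what the plan expects at that time.

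A cut halfway to zero, applied to a point estimate from a small look, will often be crossed by chance when the treatment works exactly as planned. A trial stopped this way cannot reach its primary conclusion, so power cannot exceed one minus the false-stop probability. At a given look size, that ceiling holds whatever the final sample size.

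Two ambiguities prevent a reader from knowing the trial's real power: the look size (a floor of 100 in total, or 162 per arm) and whether the rule binds.

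**Working it through.** **Inputs.** Control 20% and isoniazid 10% at 12 months (6.1.1). Linear accrual, so 10% and 5% at 6 months (6.7). Look at 50 per arm (100 in total) or 162 per arm. Final size 280 per arm (560/2), with 255 (364 less 30%) and 364 (no losses) as sensitivity cases. The test is taken as two-sided 5%; the protocol does not state sidedness.

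**1. The plan's own figures.** For 20% against 10% at 90% power, the continuity-corrected formula gives 286 per arm (572 in total), or 283 per arm (566) with unpooled variance. The stated 560 is within 3% of both, and 560 × 1.3 = 728. With 280 per arm and the pooled test, z = (0.10 − 1.96·√(2·0.15·0.85/280)) / √((0.16 + 0.09)/280) = (0.1000 − 0.0591)/0.0299 = 1.37, which is 91.4% power; simulation gives 91.9%. The Reference row's 726/1.3 = 558 matches the 20% against 10% design, confirming that the box is on the 6-month scale.

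**2. Precision at the look.** SE = √((0.10·0.90 + 0.05·0.95)/n) = √(0.1375/n), which is 5.2 points at n = 50 and 2.9 points at n = 162. The cut is (5 − 2.5)/SE = 0.48 and 0.86 standard errors below the planned gap. The normal approximation then gives stop probabilities of 31.7% and 19.5%.

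**3. Exact stop probability.** With X (control) and Y (isoniazid) independent binomials, sum P(X)·P(Y) over all pairs with (X − Y)/n < 0.025. That means an excess of at most 1 event at 50 per arm (0.025 × 50 = 1.25) and at most 4 events at 162 per arm (0.025 × 162 = 4.05).

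| Look | Stop, equal arms | Stop, simple randomization (6.1.2) | Power ceiling (1 − stop) |
|---|---|---|---|
| 100 participants | 35.4% | 32.2% | 65–68% |
| 324 participants | 22.3% | 19.6% | 78–80% |

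**4. Overall power.** One million simulated trials per setting, with 6-month events nested within 12-month events and a gap above 12.5 points counted as success. Ranges run from equal arms to simple randomization.

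| Final size per arm | No look | Look at 100, rule obeyed | Look at 324, rule obeyed |
|---|---|---|---|
| 255 | 89% | 60–63% | 73–75% |
| 280 | 92% | 61–64% | 74–77% |
| 364 | 97% | 63–66% | 77–79% |

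At 280 per arm, 87% of the stopped trials (look at 100) and 77–79% (look at 324) would have reached significance. Arithmetic check with equal arms: 91.9 − 0.354 × 87.1 = 61.1, and 91.9 − 0.223 × 78.7 = 74.3.

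**5. Does the cut do its own job?** At 162 per arm it stops only 54% of trials whose true gap is the 2.5 points it targets (10% against 7.5%).

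**6. Other readings, at 280 per arm.**
- If 2.5 points is the projected 12-month gap, the 6-month cut is 1.25 points. Wrong stops are 22–24% (look at 100) and 10–12% (look at 324), with power 72–73% and 83–85%.
- At the 26% annual infection rate in section 3 (13% against 6.5% at 6 months), wrong stops are 25–28% and 11–13%, with power 71–74% and 86–88%, against 98% without a look.

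**The case against.** The strongest points on the other side are these.

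- **The rule may not bind.** If 6.8's *may* governs, the team already has discretion and no definite power loss follows. This stands as a condition on the result. It does not remove the defect, because 6.7 says the opposite and the protocol does not choose.
- **The look could be larger.** 100 is a floor. The false-stop chance falls to 15% at 200 per arm and 11% at 280 per arm. That is correct, but the only other size printed is 162 per arm, and even at 280 per arm the ceiling is about 89%.
- **Rounding at 162 per arm.** A 4-event gap is 2.469%, which prints as 2.5%. If it is not counted as below the cut, equal-arm wrong stops are 16.4%, power is 79.4%, and the rule stops 46% rather than 54% of trials with a true 2.5-point gap. The literal reading counts it as a stop; either way power is well short of 90%.
- **It is a feasibility and sample-size check.** The insufficient rows need 3357 to 5361 participants, and "this prison unit has approximately 2,300 inmates". That is a fair reason for having a low-gap criterion. It does not remove sampling error, and the stated action is discontinuation, not re-estimation.
- **The 92% baseline counts 6-month conversions.** Section 6.5 excludes 6-month positives, and 6.6 counts conversion at month 12 or 24. If 6-month conversions are not counted, power at 280 per arm without a look is itself 62–69%, and 42–54% with the rule obeyed. The baseline here follows the one-year 20% behind 6.1.1; the stop probabilities and the ceiling are the same either way.
- **A futility stop does not inflate type I error.** True; the cost is entirely in power.

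**Conclusion.** The concern holds, conditional on the rule being obeyed. With the planned effect true, the low-gap stop wrongly ends 32–35% of trials at a look of 100 and 20–22% at 324. Overall power at 280 per arm falls from about 92% to 61–64% and 74–77%. The 90% in 6.1.1 was not reached at either printed look size, under any of the readings or final sample sizes tried. If the rule is never acted on, power stays near 92%.

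The figures assume linear accrual as stated in 6.7, a two-sided 5% test, 6-month conversions counting toward the 12-month endpoint, and 2.5% meaning the observed absolute difference at 6 months. The direction does not depend on the last two. This should be corrected, because the protocol promises a power that its own mandatory rule would not deliver.

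**What to change.** 1. Set a single look at the box's size, 162 per arm with month-6 results, and change the floor of 100 to match.
2. State that 2.5% means the observed absolute risk difference at 6 months.
3. Reconcile 6.7 with 6.8 by declaring the low-gap criterion non-binding.
4. Report in 6.1.1 the overall power with and without the rule being acted on.

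These are wording changes. Non-binding status protects power only if the rule is seldom acted on. With the look at 324 and 280 per arm, keeping 90% requires overriding about 88–89% of triggers: (90 − 74.4)/(91.9 − 74.4) = 0.89 for equal arms. Overriding half gives 83–84%.

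If the sponsor wants a binding stop, it should choose a cut and state what it costs. As one example, a cut at 0 at 162 per arm wrongly stops 3–4% and keeps about 89–90% power at 280 per arm. The price is that it stops an ineffective treatment (10% in both arms) 46% of the time instead of 80%, so more futile trials continue. That trade-off is the sponsor's to make.
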